#### **A.5. Exposures and their measurements (ketorolac versus placebo)**

All patients will have a Kalish bunionectomy performed, fixated by two 3.0 mm cannulated partially threaded screws. Patients will follow the post-operative course as outlined above. Patients will be randomized in the pre-operative holding area to either receiving ketorolac or placebo. If randomized to ketorolac, the patient will receive one 30 mg IV dose while in the operating room under anesthesia by the anesthesiologist. If not randomized to ketorolac, the patient will receive one intra-operative 30 mg IV dose of placebo by the anesthesiologist. Patients will be given the study drug (either ketorolac or placebo capsules) after the procedure. This will be dispersed from the research pharmacy department following hospital protocols. If randomized to ketorolac, the patient will take one 10 mg capsule every eight hours, beginning approximately eight hours after the surgical procedure for a total of five days (15 capsules). If randomized to placebo, the patient will take a placebo capsule every eight hours, beginning eight hours after the surgical procedure, for a total of five days (15 capsules).

#### **A.6. Randomization and Blinding**

Eligible patients will be randomized in the pre-operative holding area to either ketorolac or placebo by stratified permuted block randomization. Stratification will be by number of forefoot procedures (isolated Kalish bunionectomy versus Kalish bunionectomy plus additional forefoot procedures) and by unilateral versus bilateral (total of four possible strata: 1. Unilateral + Isolated Kalish Bunionectomy; 2. Unilateral + Kalish Bunionectomy with additional forefoot procedures; 3. Bilateral + Isolated Kalish Bunionectomy on one side; 3. Bilateral + Kalish Bunionectomy with any additional forefoot procedures. Any correlated cases will be accounted for in the analysis and are not common at this institution (but will be stratified in the event they do occur to help ensure balance between the study groups).

Study group allocation will be controlled by research pharmacy with sequentially numbered opaque sealed envelopes. This communication will occur entirely between the surgeon and research pharmacy. Allocation of ketorolac or placebo will be recorded on a "Randomization/Treatment" log that will be stored in a secure location with both opened and unopened randomization envelopes.

Access to this secure location will be controlled and locked. A coded master list will be kept in a locked and secured cabinet.

Patients, surgeons, anesthesiologists, and any assessors will be blinded. Only research pharmacy will not be blinded. Both ketorolac and placebo capsules and bottles and intra-venous preparations will appear exactly the same and will be prepared by research pharmacy. Assessors will be collecting data on post-operative pain and radiographic unions and will not be made aware of the patient's randomization results. In the event of an emergency or where the subject safety may be at risk, research pharmacy will unblind any necessary individuals to properly care for patients. In this event, the details of revealing the assigned study drug must be recorded in the subject's source documents.

#### **A.7. Study Endpoints**

The study will be concluded once each patient achieves radiographic union at 12 weeks (please refer to grading scale in the statistical consideration section) or up to six months, whichever comes first. If a patient experiences a serious adverse event, requiring them to discontinue the study medication, they will be immediately withdrawn from the study, treated appropriately, and reported.

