study, however, the surgeon may deviate intra-operatively based on the following guidelines (we do not anticipate any significant surgical technique deviations): failure to achieve adequate compression, intra-operative complication necessitating change in fixation, less than 60-70% of bone-to-bone contact of capital fragment to remaining metatarsal head and shaft, surgeon preference. Any intra-operative deviations will be recorded and accounted for in the analysis. No orthobiologic applications (i.e. bone stimulators or artificial/autologous graft) will be used. If it is known to the surgeon that the patient will require orthobiologic applications, the patient is not eligible for enrollment in this study. Of note, orthobiologic applications such as bone stimulators or bone graft are not traditionally used and are considered unnecessary for this bunionectomy procedure. The remaining medial bony shelf is removed and soft tissue rebalancing is performed as needed. A medial capsulorrhaphy is performed. The remaining capsule and soft tissue is sutured closed. The skin closure is based on surgeon preference, but is traditionally a running subcuticular closure using 4-0 monocryl suture. A soft, compressive, sterile dressing will then be applied and the tourniquet is then released.

**The surgical technique described above, the surgical dressing, and the post-operative care are all considered standard of care for this procedure. The only study specific procedures include telephone calls, study drug, patient diaries, and questionnaires (which will be described in subsequent sections).**

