**frequency of clinic visits are all standard of care and do not change as a result of this study.**

The surgeon may deviate if he/she feels it is necessary for a particular patient or if concomitant procedures necessitate a deviation. Any deviations will be recorded and accounted for in the analysis. We do not anticipate any significant protocol deviations. Immediate anteroposterior and lateral radiographs will be taken post-operatively. The patient will be placed in a sterile soft post-operative dressing. Research pharmacy will dispense the study medication (oral ketorolac or placebo) and standardized prescriptions will be given for opioid pain medication. Standard post-operative instructions will be given to all patients. This includes instructions for icing and elevating the foot, as well as medication instructions. Patients will be allowed to partial weight bear in a post-operative shoe with crutches due to the inherent stability of the osteotomy, given that rigid internal fixation is provided as detailed in the surgical technique. Patients will be given a study diary with instructions on how to properly record information. The post-operative care described here is considered standard of care for this procedure (except for the study drug and study diary) and not related to the study.

*c. Day Two:* Patients will be contacted by telephone two days (48 hours,  $\pm 4$  hours after the surgical procedure) by a dedicated research fellow trained in survey administration between the hours of 8am and 6pm. This person has no involvement with the surgical procedure and is blinded to the patient's randomization status. This will allow enough time for the affects of anesthesia to subside, 48 hours ( $\pm 4$  hours) following his/her surgery. This will also be well within the five day window in which the patient will be taking ketorolac post-operatively.

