*h. Week Twelve and Subsequent Visits:* Weight bearing anteroposterior and lateral foot radiographs will be taken and the patient will be clinically assessed at week twelve  $\pm$ 1 week. If there is complete osseous union on radiographs, the patient will have completed the study. If there is incomplete osseous union on radiographs, the patient will continue to be followed by his/her surgeon. The timing and frequency of these subsequent visits will be determined by the patient's surgeon.

If there is incomplete osseous union after twelve weeks, the patient will be classified as a delayed union. If there is incomplete osseous union after six months, the patient will be classified as a nonunion.

**The post-operative care described here is considered standard of care for this procedure (except for the study drug, telephone call, study diary, and questionnaires) and not related to the study.**

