### **B. Statistical Considerations**

#### **a. Sample Size Justification:**

In performing the required sample size calculations, the authors assumed that potential cluster effects may be evident as a function of the individual surgeon. Because of this likelihood of cluster effects, we estimate the power of the study for change in post-operative pain that assumes an intra-class correlation (ICC) of at least 0.08 to inflate sample size estimates. This assumes 80% power to detect differences between groups with a 0.05 two-sided significance. Previous literature reports that in comparisons of opioid alone versus ketorolac with opioid the mean difference was observed to be 1.8 on the VAS (16). The widely accepted minimum clinically significant pain relief has been reported to be 1.3 (17). Detection of a 1.3 absolute difference in change in pain relief between groups requires 40 patients per group; detection of a 1.8 difference requires 20 patients per group consisting of eight and four (surgeons) respectively, assuming clusters of 10 subjects each. These calculations use an extremely high ICC which maximizes its accuracy. Because of the unknown ICC influence, a sensitivity analysis was performed assuming a non-contributory ICC of 0.08 which required a total sample size of 20 subjects per arm using the smallest clinically significant difference to detect.

Based on these calculations the largest sample required is 80 subjects. In order to preserve statistical power in the face of drop-outs and patient contact difficulties, the total sample size will be inflated by 10% such that the final projected sample size will be 88 subjects, or 44 per arm.

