**Thus, the previously noted 88 total sample size (44 patients per treatment arm) was estimated to**

**be adequate to achieve study aims and goals.**

**b. Data Analysis**

**Outcomes and their Measurements**

*a. Primary Outcome*

All analyses will be calculated using Statistical Analysis Software (SAS, Worldwide Headquarters, Cary, NC) and will be based on the **intention-to-treat principle**.

The primary outcome of interest is pain measured on the second post-operative day, 48 hours ( $\pm 4$  hours) following surgery. This will allow the effects of anesthesia to subside following surgery. This will be well within the five day window in which the patient will be taking ketorolac post-operatively.

Pain will be measured by both unidimensional and multidimensional instruments. A blinded trained research fellow will contact patients by telephone and will administer the McGill Pain Questionnaire-Short Form (MPQ-SF) and instruct patients to fill out the visual analog scale (VAS). This will occur 48 hours ( $\pm 4$  hours) post-operatively. The VAS will be pre-printed in a diary that is given to the patient post-operatively. The VAS will be 10 cm in length with the end anchors, "no pain" and "worst pain possible". If patient compliance with the VAS is greater than 95%, then the VAS will be used for the primary analysis. As a back-up, the MPQ-SF will be utilized as the primary analysis. Regardless, sensitivity analyses will be conducted to verify the robustness of the results. The research fellow will also obtain the patient's post-operative pain medication consumption (including timing and dosages) and verbally confirm study protocol compliance during this telephone interview (Please refer to the variables collected section for full details; A telephone script is also included in this IRB application). Regression will be utilized to control for measured confounders, including timing of the telephone interview and last dose of post-operative pain medication. Standard regression model rules will be applied and a p-value  $\leq 0.05$  will be considered statistically significant in the final regression model.

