The patient diaries with the VAS will be collected during the first post-operative visit (one week). Patients will be asked to bring all surgery related medications and bottles to this post-operative appointment. The research fellow will again obtain the patient's post-operative pain medication consumption (including timing and dosages) by counting pills and verbally confirm study protocol compliance (Please refer to the variables collected section for full details).

Whether a difference in delayed unions at twelve weeks exists between the two groups will also be assessed. Radiographic union for each patient will be assessed by both a blinded, board-certified radiologist and two blinded board-certified podiatric surgeons. Agreement between these three experts will be assessed with a kappa score and the mean result will be used for primary analysis. Delayed and non-union rates will be compared between the two groups. A previously documented scoring system found to have both high inter- and intra-observer reliability in a series of tibial fractures reduced surgically will be utilized for this assessment. This scoring system grades each fracture according to four characteristics: 1. Rating of fracture healing, 2. Callus morphology, 3. Number of cortices visible or obliterated. 4. Number of cortices bridged (41). The modification utilized for this study will be as follows:

- ❖ **Grade 1:** Homogenous bone structure with complete obliteration of fusion site
- ❖ **Grade 2:** Massive bone trabeculae crossing fusion site, 3-4 cortices are bridged with fusion site barely discernable
- ❖ **Grade 3:** Apparent bone trabeculae crossing fusion site, 2-3 cortices are bridged with fusion site discernable
- ❖ **Grade 4:** Trace bone trabeculae crossing fusion site, 1-2 cortices are bridged with distinct visible joint space

- ❖ **Grade 5:** No bone trabeculae crossing fusion site, 0 cortices are bridged with complete visible joint space

A delayed-union will be defined as a grade 4 or 5 in any patient over twelve weeks. A nonunion will be defined as a grade 4 or 5 in any patient over six months. Analysis will include logistic regression for these binary endpoints. Odds ratios and 95% confidence intervals will be calculated between groups (delayed and/or non-union: yes/no). A 2-sided p value of  $\leq 0.05$  will be considered statistically significant.

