#### **Missing Data**

Given that the first outcome measure occurs within two days and the second outcome occurs in twelve weeks of study enrollment, we do not anticipate that missing data will be a large concern. Protocol deviations will be recorded and reported but the primary analysis will be an **intent-to-treat analysis**. For outcomes requiring a longer follow-up duration, any patients who are lost, move or expire will be counted as treatment failures. Patients will be generally healthy as this is a population undergoing elective bunionectomy surgery. In addition, information will be collected regarding patient contact information to help prevent loss of patients. Patients that miss a follow-up appointment will have a set mechanism in-place in order to contact the patients. All available contact information

including the patient's residential and work address, work, home and cellular phone number as well as contact information of the next of kin and closest friend will be obtained for each patient. Permission to contact these people as necessary will be obtained. The short follow-up period will also improve success in these measures. Finally, there is a built in 10% increase in patient sample size if the above safety measures still fail.

Although we do not anticipate significant missing data problems, any concerns will be dealt with sensitivity analyses to determine their impact.

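### A drug-stopping serious adverse event removes the patient from the study, so an early event can lose the primary 48-hour pain score despite the declared intention-to-treat analysis

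*Combined protocol and SAP*

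**What the plan says.** The rule is in section A.7, Study Endpoints: "If a patient experiences a serious adverse event, requiring them to discontinue the study medication, they will be immediately withdrawn from the study". The same sentence adds that the patient is treated and the event reported. It mentions stopping the medication separately, so leaving the study is a further step.

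Four other parts of the document bear on it.

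- **What belongs to the study and what is routine.** Section A.3 states: "The only study specific procedures include telephone calls, study drug, patient diaries, and questionnaires". For the rest of post-operative care, radiographs included, section A.4 b says that the "frequency of clinic visits are all standard of care and do not change as a result of this study". Section B5 adds that films go into the hospital's online record.
- **Analysis principle.** Both Data Analysis and Missing Data declare intention-to-treat. Neither mentions withdrawn patients.
- **Missing outcomes.** The Missing Data section has one imputation rule: "For outcomes requiring a longer follow-up duration, any patients who are lost, move or expire will be counted as treatment failures". Beyond that it promises sensitivity analyses, without saying which.
- **Other adverse events.** Section B5 tells a patient with an event thought to be due to ketorolac to stop the drug and contact the surgeon. Whether the patient leaves the study is a separate decision for the surgeon.

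**The concern.** Intention-to-treat needs outcomes from all randomised patients, including those who stop treatment early. A.7 ends study participation for exactly the patients who stop because of a serious event, and such events may be commoner in one arm than the other. If their outcomes go missing, the comparison is no longer fully protected by randomisation. The drop-out allowance restores numbers but does not remove a bias of this kind.

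The primary outcome is the most exposed. The 48-hour score is collected while patients are still on study drug, so an event that stops the drug can come before it. Routine care has no equivalent measurement.

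**Working it through.** **1. Each outcome set against the rule**

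- *48-hour pain, event before the call.* The call, questionnaire and diary are study procedures. If A.7 is followed, they do not take place and nothing replaces them. The failure rule is limited to longer follow-up and to patients who are lost, move or die, so it does not reach this score. A sensitivity analysis cannot recover a score that was never taken.
- *48-hour pain, event after the call.* The MPQ-SF has been recorded by telephone and the VAS form would normally have been completed. It can be handed in at the routine week-one visit. The open question is whether it is used.
- *12-week union.* The visit and film are routine, so the film would normally exist. The open question is whether it is graded and analysed.

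**2. The plan's own numbers**

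Sample Size Justification says that "the total sample size will be inflated by 10% such that the final projected sample size will be 88 subjects, or 44 per arm". This reproduces: 80 × 1.10 = 88. The allowance is 88 − 80 = 8 patients.

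**3. Expected number losing the 48-hour score**

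From the documents: 88 patients; dosing over 5 days = 120 hours; call at 44 to 52 hours. Assumptions, because the documents give neither: 1 to 5% of patients have such an event, and events are spread evenly over dosing.

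- Patients with an event, both arms together: 88 × 0.01 = 0.88 to 88 × 0.05 = 4.4.
- Share of events before the call: 44/120 = 36.7% to 52/120 = 43.3%.
- Expected scores lost: 0.88 × 0.367 = 0.32 to 4.4 × 0.433 = 1.91.

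These are means. At the upper inputs the chance per patient is 0.05 × 52/120 = 0.0217. The binomial probability of three or more among 88 is then about 30%.

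**4. Possible shift in an arm mean**

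If k patients of 44 are lost and their scores lie d points from the arm mean, the mean of the rest moves by k × d/(44 − k). The values of k and d are assumptions.

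- k = 1, d = 2: 2/43 = 0.05 VAS points.
- k = 2, d = 4: 8/42 = 0.19.
- k = 3, d = 4: 12/41 = 0.29.

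The plan's target difference is 1.3. The sign depends on which arm loses scores and whether those patients had more or less pain; the documents settle neither.

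**5. Why the use of films should be settled in advance**

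One patient counted as a failure moves an arm by 1/44 = 2.3 percentage points. Suppose 1, 2 or 3 observed delayed unions in each arm of 44 (assumption), and one withdrawn patient in one arm whose film is not used.

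- Counted as a failure, the odds ratio is (2 × 43)/(42 × 1) = 2.05, (3 × 42)/(41 × 2) = 1.54 or (4 × 41)/(40 × 3) = 1.37.
- Excluded (43 against 44), it is about 1.02 in each case.

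None of these is close to significance (Fisher p = 1.0 for the failure counts), but the estimate does depend on an unstated choice.

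**The case against.** The best defence is that A.7 is a safety instruction, not an analysis rule. It does not say that data collection ends, and intention-to-treat is declared twice. No visible text excludes withdrawn patients from analysis, and investigators might well go on following them. Eligibility is also designed to keep out those at greatest risk from ketorolac. Part of this stands: for forms and films that exist, intention-to-treat already points to using them, and few patients are likely to be affected. It does not answer the early event, because an analysis principle cannot supply a score that the rule led staff not to collect.

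A second objection is that section B7 and the consent form are not in the text examined. That stands as a limit: the point is that no visible section provides for follow-up, not that none exists.

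Two stronger readings are tempting.

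- *All later outcomes of these patients are lost.* The documents do not support this. Visits and films are standard of care, and the films enter the hospital record.
- *The rule could change the primary instrument.* The plan says: "If patient compliance with the VAS is greater than 95%, then the VAS will be used for the primary analysis". Since 84/88 = 95.5% passes and 83/88 = 94.3% does not, four missing forms are tolerated, and a reader might infer that four withdrawals would use them up. On the even-timing assumption, however, 57 to 63% of events follow the call, so 2.3 to 2.5 of four such patients would already have completed the form. The plan also does not say whether withdrawn patients count in the denominator.

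**Conclusion.** The point holds as a minor one. Followed as written, A.7 can lose the primary pain score of a patient whose serious event precedes the day-two call, for a reason that may depend on treatment. That conflicts with the declared intention-to-treat analysis. For completed diary forms and 12-week films, the gap is only whether they are used.

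The expected loss of 0.3 to 1.9 scores among 88 rests entirely on the assumed event rate and even timing. It should not be read as a maximum of two, nor the shifts in the arm mean as bounds. An expected loss of this size lies well within the 8-patient allowance, so the issue is bias rather than power. The effect is probably small and its direction unknown. Nothing in the documents shows that a conclusion of the trial would change.

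**What to change.** Reword A.7 so that a serious adverse event requiring discontinuation stops study drug only. The patient continues the day-two call, diary return, visits and radiographs, and is analysed in the assigned arm. The exceptions are withdrawal of consent and the withdrawal rule in the Pregnancy section.

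State that diary forms and films that exist are used. Under Missing Data, apply the failure rule to such a patient only when no film can be obtained, and add a sensitivity analysis that excludes these patients.

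Leave section B5 as it is: the surgeon's discretion and emergency unblinding are safety provisions, and no fault in them has been shown. The clinical rule for stopping the drug also stays the same.

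The cost is a wording change and minor follow-up effort, namely a telephone call and a diary return per affected patient. Visits and films already take place as routine care.
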